6.2 IMPORTANT PROTOCOL DEVIATIONS

According to (3) important safety protocol deviations (iPDs) are those that potentially affect the rights or safety of study subjects. Important PDs are those that can potentially influence the primary outcome measure(s) for the respective patients in a way that is neither negligible nor in accordance with the study objectives.

No per protocol set is defined for this phase I trial, but patients with important protocol deviations (iPD) will be identified and reported in the clinical trial report (CTR). Potential IPDs are defined in [Table 6.2: 1](#). The final list of IPDs will be confirmed at the last report planning meeting (RPM) before DBL.

Data discrepancies and deviations from the CTP will be identified for all treated patients. Listings of protocol deviations and of unresolved discrepancies will be provided to be discussed at the medical quality review meetings (MQRMs), e.g. deviations in drug administration, in blood sampling etc. At these meetings, it will be decided whether the discrepant data can be used as they are or whether the data have to be corrected in the clinical database.

Each protocol deviation must be assessed to determine whether it is an important protocol deviation. A protocol deviation (PD) is important if it affects the rights or safety of the study patients or if it can potentially influence the primary outcome measure(s) for the respective patients in a way that is neither negligible nor in accordance with the study objectives. PDs that do not influence the patient's rights and safety or the evaluability of the patients for the main study objectives are called non-important PDs. These are only considered when checking the trial quality in general.

If any manual iPDs are identified, they are to be summarised into categories and will be captured in the MQR/RPM minutes via an accompanying Excel spreadsheet (3). The following table ([Table 6.2: 1](#)) contains the categories which are considered to be possible IPDs in this trial.

Table 6.2: 1 Important protocol deviations

Category / Code	Description	Comment/Example	Excluded from	Automatic /manual
-----------------	-------------	-----------------	---------------	-------------------

A		Entrance criteria not met			
	A1	Patient has condition that may cause additional risk from study medication		None	Automatic
	A2	Patient has laboratory assessment that may cause additional risk		None	Automatic
	A3	Patient is unable to comply with the protocol		None	Automatic
	A4	Patient does not have trial diagnosis or is not part of the target population		None	Automatic
	A5	Patient has condition that may interfere with evaluation of safety and/or efficacy		None	Automatic
B		Informed consent			
	B1	Informed consent not available, not done		All	Automatic
	B2	Informed consent too late	Date of informed consent later than the first study related procedure (This does not include the informed consent for biobanking.)	None	Automatic
C		Trial medication			
	C1	Incorrect treatment administered	Study medication dispensing error leading to change in actual treatment	Decision at MQRM	Automatic
	C2	Continuation/Discontinuation of study medication not according to protocol		Decision at MQRM	Automatic
D		Concomitant medication			
	D1	Prohibited medication	Based on restrictions regarding concomitant treatment as specified in CTP Section 4.2.2.1	None	Manual
E		Trial specific violations			
	E1	Incorrect study procedures performed	Any deviation from the protocol not defined above but deemed important to be documented in the CTR	Decision at MQRM	Manual

6.3 SUBJECT SETS ANALYSED

Screened Set (SCS)

[figure not shown]
This patient set includes all patients who have signed the informed consent. The screened set will be used for patient disposition tables.

Treated Set (TS)

This patient set includes all patients who were documented to have received at least one dose of [⁸⁹Zr]Zr-BI 754111, BI 754111, or ezabenlimab. The TS will be used for all safety and efficacy analyses including the primary analysis.

Pharmacokinetic Analysis Set (PKS)

All evaluable patients in the TS which provide at least one evaluable observation for at least one PK endpoint and no PK relevant protocol violation. PKS is used for pharmacokinetical analysis.

6.5 POOLING OF CENTRES

This section is not applicable, because the study was performed in only one center.

6.6 HANDLING OF MISSING DATA AND OUTLIERS

Missing or incomplete AE dates are imputed according to BI standards (see “Handling of missing and incomplete AE dates”) (4).

Potential outliers will be reported and analyzed as observed. In general, missing data not discussed in (4) and (2) will not be imputed unless required for the following analyses and definitions. Then the rules as described below apply.

1) Change of laboratory values from baseline

Laboratory values at baseline: For missing laboratory data at cycle 1 day 1 (before the first administration of any study medication) the data of preceding visits will be used if available.

2) Definition of on-treatment period and actual treatment

Date of permanent discontinuation of study medication: All reasonable efforts should be undertaken during the study to obtain the dates of permanent discontinuation of

study medication. However, if the date of the very last administration is missing this will be imputed with:

- If only month and year are given, the last day of the month will be used for imputation
- If only the year is given, the 31st of December of this year will be used for imputation

If the imputed date leads to a date that is later than the date of the EOT visit, then the imputed date is the date of the EOT visit. If the imputed date leads to a date that is later than the death date, then the imputed date is the date of death.

3) Partial death dates

If a partial (year and month) death date is reported, the date will be imputed with the end of the month. This is in line with the imputation of partial dates for the analysis of AEs.

For descriptive statistics: Dates will not be imputed if more than only the day of the date is missing.

6.7 BASELINE, TIME WINDOWS AND CALCULATED VISITS

Study days and visits will be labelled according to the flowchart of the CTP. For nominal time points and windows of tumor imaging, see [Table 6.7: 1](#).

Unless otherwise specified, baseline is defined as the time point closest but prior to the very first administration of any study medication. If no time is specified and the date is the same as the first administration date, then it will still be considered baseline if not specified otherwise. If there is no measurement earlier than the first administration of study medication, then no baseline will be derived.

Note that for some trial procedures (for example Eastern Co-operative Oncology Group (ECOG) performance score, body weight, vital signs, laboratory tests) this may be the value measured on the same day when trial medication was started. In these cases it will be assumed that the measurements were taken prior to the intake of any study medication.

Study day will be calculated relative to the date of the first administration of study drug. The day prior to first administration of study drug will be ‘Day -1’ and the day of first administration of study drug will be ‘Day 1’ ; therefore ‘Day 0’ will not exist.

[REDACTED]

[REDACTED]

[REDACTED]

Laboratory values:

Baseline is defined as the latest time point before the very first administration of any study medication. For laboratories where not only the examination date but also time are recorded, examination time has to be taken into account when defining baseline. That is, a laboratory value on the same date as the first administration of study medication is considered as baseline value if and only if the time of laboratory assessment is before or the same as the time of first study drug administration.

If any of these times is missing and the date of laboratory assessment is equal to the date of first administration of study medication, then the laboratory assessment will be considered as according to protocol, i.e. as prior to first study medication.

7. PLANNED ANALYSIS

The labelling and display format of statistical parameters will follow the guideline “Reporting of Clinical Trials and Project Summaries” ([7](#)).

For End-Of-Text (EoT) tables, the set of summary statistics is: N / Mean / SD / Min / Median / Max.

For tables that are provided for endpoints with some extreme data, median, quartiles and percentiles should be preferred to mean, standard deviation, minimum and maximum.

Tabulations of frequencies for categorical data will include all possible categories and will display the number of observations in a category as well as the percentage (%) relative to the respective treatment group (unless otherwise specified, all subjects in the respective subject set whether they have non-missing values or not).

The precision for percentages should be one decimal point, unless the denominator is smaller than 100 (in all treatment columns), in which case percentages are given in integer numbers. The category missing will be displayed only if there are actually missing values.

Sort order for general categorical variables: If categories correspond to the collected categories on the eCRF and the table shells do not explicitly specify the ordering, the “default ordering” defined by the eCRF is to be used in such cases. If categories are derived, the ordering as specified in the table shell document should be used; in general ordinal data (e.g. categorised continuous data) are to be displayed in ascending order.

The denominator of the main categories is defined by the number of patients in the used patient set. The main categories define the denominators of the subcategories. Subcategories should be intended and "[N(%)]" to be displayed only for the main category.

If a table includes only categorical data, "N[(%)]" is to be displayed in the column header only.

Abbreviations (e.g. Wors.) should not be displayed without any explanations. They will be either spelled out in the table or explained in footnotes (whatever is more reasonable from the programming point of view).

If applicable, conversion from days to weeks, months and years will be as follows:

- Weeks = Days/7
- Months = (Days × 12)/365.25
- Years = Days/365.25

7.1 DEMOGRAPHIC AND OTHER BASELINE CHARACTERISTICS

Only descriptive statistics are planned for this section of the report. Demographic parameters collected and to be presented include

- Sex (Male, Female)
- Race and ethnicity (as defined in the eCRF)
- Age [years]
- Height [cm]
- Weight [kg]
- Body mass index [kg/m²] (defined as weight [kg]/(height [cm]/100)²)
- Smoking history (Never, Current, Former)
- Baseline ECOG
- Site
- Country

Descriptive statistics are planned for disease history, prior anti-cancer therapies, medical history and baseline disease assessment.

7.2 CONCOMITANT DISEASES AND MEDICATION

Only descriptive statistics are planned for this section of the report.

Concomitant diseases will be coded similarly as AEs based on the most current Medical Dictionary for Regulatory Activities (MedDRA) version.

Concomitant therapies (CTs) will be coded according to World Health Organization Drug Dictionary (WHO DD). CTs will be classified according to the Anatomical Therapeutic Chemical (ATC) classification system. The third ATC level will be used to categorise CTs by therapy type. In situations where a medical product may be used for more than one equally important indication, there are often several classification alternatives. As appropriate, patients receiving CTs with more than one possible ATC level 3 category will be counted more than once. Footnotes will clarify this possible double counting in tables.

7.3 TREATMENT COMPLIANCE

Not applicable in this study.

7.4 PRIMARY ENDPOINT(S)

All evaluations will be based on the treated set (TS), unless otherwise stated. Patients who might not be evaluable for the assessment of [⁸⁹Zr]Zr-BI 754111 (Cycle1 and Cycle2) will be excluded from the primary endpoint analysis. Exclusion of a subject's data will be documented in the clinical trial report (CTR).

The primary endpoint will be analyzed descriptively.

7.4.1 Primary analysis of the primary endpoint(s)

The primary endpoint is defined as:

Mean relative change ($\Delta\text{SUV}_{\text{peak}}$) of the standardized uptake values (SUV_{peak}) from baseline (Cycle1 / C1) to on-treatment (Cycle2 / C2) PET assessments in all evaluable, metabolic active lesions.

Two PET imaging time points (PET assessments) will be considered for the calculation (2 time points for CTP v1/v2; 3 time points CTP v3/not applicable); the time point leading to the maximum effect (max. reduction from baseline) will be reported.

Calculation:

The primary endpoint is derived for each patient as follows:

- Calculate the relative change from baseline for each selected lesion at each time point (e.g. 96h, 144h):
$$100 * (\text{SUV}_{\text{peak,lesion,timepoint,C2}} - \text{SUV}_{\text{peak,lesion,timepoint,C1}}) / \text{SUV}_{\text{peak,lesion,timepoint,C1}}$$
- Calculate the mean over all evaluable lesions (at each time point)
- Select the lower mean, i.e. choose the time point with maximum average effect/reduction in tumor uptake from baseline ($= \Delta\text{SUV}_{\text{peak}}$)

The minimum mean $\Delta\text{SUV}_{\text{peak}}$ will be summarized per cohort (dose group of BI 754111 in Cycle2) as: N / Mean / SD / Min / Median / Max.

A similar analysis of minimum mean $\Delta\text{SUV}_{\text{peak}}$ will be presented for each patient as: N / Mean / SD / Min / Median / Max.

Tumor uptake at baseline:

The mean tumor uptake at baseline will be summarized per cohort (blocking dose of BI 754111 in Cycle2) separately for each imaging time point (96h, 144h) as the mean $\text{SUV}_{\text{peak,C1}}$ over all selected lesions as: N / Mean / SD / Min / Median / Max.

A similar analysis of mean tumor uptake (SUV_{peak}) at baseline (Cycle1) will be presented for each patient as: N / Mean / SD / Min / Median / Max.

Impact of CTP amendments:

As per CTP v3, the assessment of the primary endpoint was changed from 2 to 3 PET scans (imaging time points) to assess tumor uptake. The changes are not considered to impact on the primary endpoint; the reported effect is assumed to be fully captured in the time window. No patients were actually imaged as per CTP v3.

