4. Tumor biopsy: 2 core needle tumor biopsies (or equivalent) are to be taken from an imageable and evaluable lesion prior to first BI 754091 administration, unless medically contraindicated. In the latter case, 25 4 μ m-sections from an archival biopsy taken at relapse after the previous treatment are acceptable. For PD-1/PD-L1 pre-treated patients, if available, 5 sections of an archived tumor biopsy taken prior to the anti-PD-1/PD-L1 treatment should be obtained. *Optional: one, if feasible, two biopsies (2 core needle biopsies each) are to be taken for autoradiography and Flow cytometry analysis within 48h after the last $[^{89}\text{Zr}]\text{Zr-BI 754111}$ PET scan of C1. The biopsies are to be taken from two different lesions based on the results of the PET scans: one lesion with tracer uptake (= positive) and one lesions without visible tracer uptake (= negative). See [Section 5.4.1](#) for details.*
5. Biomarker (BM) blood sampling for immunophenotyping is to be done at Cycle1 Day1 and Day7 \pm 1 day post $[^{89}\text{Zr}]\text{Zr-BI 754111}$, at Cycle2 Day1 (prior to BI 754111 treatment infusion) and Day 7 \pm 1 day post $[^{89}\text{Zr}]\text{Zr-BI 754111}$ (=Cycle 2 Day7 \pm 1 day for LAG-3 negative patients), Cycle3 Day1 and EOT. See [Blood Sample Flow Chart](#) for time schedule.
6. Blood sampling for BI 754111 PK concentration will be performed at Cycle1 “baseline assessment phase” (before $[^{89}\text{Zr}]\text{Zr-BI 754111}$ infusion, after $[^{89}\text{Zr}]\text{Zr-BI 754111}$ infusion and during the first and each subsequent PET scan procedure, at Cycle2 “on-treatment assessment phase” (pre-treatment, after $[^{89}\text{Zr}]\text{Zr-BI 754111}$ infusion and at each PET scans procedures, at Cycles 3, 4, 7 (prior to BI 754111 treatment infusion) and at the EOT visit. See [Blood Sample Flow Chart](#) for a more detailed time schedule.
7. **Timing of baseline assessment procedures** for $[^{89}\text{Zr}]\text{Zr-BI 754111}$ PET scanning:
 - $[^{89}\text{Zr}]\text{Zr-BI 754111}$ is to be administered no later than day 8 (within day 1 to 8)
 - **Only for patient in Part 1:** PET/CT scan for dosimetry is to be done 1-2 hours after $[^{89}\text{Zr}]\text{Zr-BI 754111}$ administration
 - $[^{89}\text{Zr}]\text{Zr-BI 754111}$ PET for LAG-3 combined with low dose CT scan for tumor volume: 2 (before CTP 3.0)-3(after CTP 3.0) scans between 24 h and up to 7 days post $[^{89}\text{Zr}]\text{Zr-BI 754111}$ injection

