12. *Pre-treatment (antihistamine and acetaminophen or paracetamol) should be administered at sufficient time prior to initiation of infusion to allow the agents to exert their influence*
13. *Visits only applicable after CTP v 3.0*

For further details on procedures, please refer to specific sections in the protocol.

BLOOD SAMPLE FLOW CHART

Table 1

Time schedule for PK, ADA and biomarker blood sampling in Cycle 1 (*before CTP amendment 2.0*)

Treatment Cycle	Visit	Time Point Description	PK BI 754111	ADA BI 754111	BM Immuno-pheno-typing	PK Radioactivity
1	1	Day 1, within 1 hour prior to BI 754091 infusion	x	x	x	
		BI 754091 infusion				
	2	within 8 days after BI 754091 infusion: [⁸⁹ Zr]Zr-BI 754111 infusion				
		1 hour after [⁸⁹ Zr]Zr-BI 754111 infusion	x			
		within 30 min before Dosimetry PET scan*				x*
		1-2 hours after [⁸⁹ Zr]Zr-BI 754111 infusion: Dosimetry PET scan*				
		within 30 min before PET scan 1	x			
	3	≥24hours post [⁸⁹ Zr]Zr-BI 754111 PET scan 1				x
		within 30 min before PET scan 2				x
	4	≤ 7 days post [⁸⁹ Zr]Zr-BI 754111 PET scan 2				

* Only for patients in Part 1, not applicable in Part 2

ADA = anti-drug antibodies; PK = Pharmacokinetics; EOT = end of treatment

Proprietary confidential information © 2020 Boehringer Ingelheim International GmbH or one or more of its affiliated companies

Table 2

Time schedule for PK, ADA and biomarker blood sampling in Cycle 2 and onwards (*before CTP amendment 2.0*)

Treatment Cycle	Visit	Time Point Description	PK BI 754111	ADA BI 754111	BM Immuno-pheno-typing	PK Radioactivity
2	1	Day 1, within 1 hour prior to BI 754091 + BI 754111 infusion			x	
		BI 754091 + BI 754111 infusion				
		after BI 754091 + BI 754111 infusion: [⁸⁹ Zr]Zr-BI 754111 infusion**				
		1 hour after [⁸⁹ Zr]Zr-BI 754111 Infusion**	***			
	2	within 30 min before PET scan 1	***			
		≥24hours post [⁸⁹ Zr]Zr-BI 754111 PET scan 1				x**
	3	within 30 min before PET scan 2**	***			
					x**	
		≤ 7 days post [⁸⁹ Zr]Zr-BI 754111 PET scan 2**				x**
3	1	Day 1, within 1 hour prior to BI 754091 + BI 754111 infusion			x	
4	1	Day 1, within 1 hour prior to BI 754091 + BI 754111 infusion	x	x		
7	1	Day 1, within 1 hour prior to BI 754091 + BI 754111 infusion	x	x		
EOT	EOT	at treatment discontinuation	x	x	x	

** These procedures are not applicable in Part 2 for patients with tumor tested negative for LAG-3 expression except the sample for immunophenotyping that should be taken at day7 (± 1day)

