Proprietary confidential information © 2020 Boehringer Ingelheim International GmbH or one or more of its affiliated companies

Table 3

Time schedule for PK, ADA and biomarker blood sampling in Cycle 1 (after CTP amendment 2.0)

Treatment Cycle	Visit	Time Point Description	PK BI 754111	ADA BI 754111	BM Immuno-pheno-typing	PK Radioactivity
1	1	within 3 hours prior to BI 754091 infusion	x	x	x	
		BI 754091 infusion				
	2	within 8 days after BI 754091 infusion: [⁸⁹ Zr]Zr-BI 754111 infusion				
		+ 5 min post end of [⁸⁹ Zr]Zr-BI 754111 infusion	x			x
		+ 30 min post end of [⁸⁹ Zr]Zr-BI 754111 infusion	x			x
		+ 60 min post end of [⁸⁹ Zr]Zr-BI 754111 infusion	x			x
		+ 120 min post end of [⁸⁹ Zr]Zr-BI 754111 infusion	x			x
	3	Planned time ~+24hs (within 1 to 2 days) post [⁸⁹ Zr]Zr-BI 754111 PET scan 1				
		within 30 min after PET scan 1	x			x
	4	Planned time ~+48hours (within 2 to 4 days) post [⁸⁹ Zr]Zr-BI 754111 PET scan 2				
		within 30 min after PET scan 2	x			x
	5	Planned time ~+96 hours (within 4 to 7 days) post [⁸⁹ Zr]Zr-BI 754111 PET scan 3				
		within 30 min after PET scan 3	x			x
		At day 7± 1day			x	

ADA = anti-drug antibodies; PK = Pharmacokinetics; EOT = end of treatment

Proprietary confidential information © 2020 Boehringer Ingelheim International GmbH or one or more of its affiliated companies

Table 4

Time schedule for PK, ADA and biomarker blood sampling in Cycle 2 and onwards (after CTP amendment 2.0)

Treatment Cycle	Visit	Time Point Description	PK BI 754111	ADA BI 754111	BM Immuno-pheno-typing	PK Radioactivity
1	1	within 3 hour prior to BI 754091 + BI 754111 infusion	x	x	x	
		BI 754091 + BI 754111 infusion				
		after BI 754091 + BI 754111 infusion: [⁸⁹ Zr]Zr-BI 754111 infusion**				
		+5 min post [⁸⁹ Zr]Zr-BI 754111 infusion**	x**			x**
		+30 min post [⁸⁹ Zr]Zr-BI 754111 infusion**	x**			x**
		+60 min post [⁸⁹ Zr]Zr-BI 754111 infusion**	x**			x**
		+120 min post [⁸⁹ Zr]Zr-BI 754111 infusion**	x**			x**
2	2**	Planned time ~+24hs (within 1 to 2 days) post [⁸⁹ Zr]Zr-BI 754111 PET scan 1**				
		within 30 min after PET scan 1**	x**			x**
	3**	Planned time ~+48hours (within 2 to 4 days) post [⁸⁹ Zr]Zr-BI 754111 PET scan 2**				
		within 30 min after PET scan 2**	x**			x**
4**	4**	Planned time ~+96 hours (within 4 to 7 days) post [⁸⁹ Zr]Zr-BI 754111 PET scan 3**				
		within 30 min after PET scan 3**	x**			x**
		At day 7± 1day			x	

Table 4

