5.6 OTHER ASSESSMENTS

5.6.1 FDG-PET/CT procedure

A standard static diagnostic FDG-PET will be performed during screening for the assessment of tumor viability and necrosis. This procedure will be performed in accordance with European Association of Nuclear Medicine (EANM) FDG-PET/CT procedures guidelines for tumor imaging ([R18-1536](#)).

5.6.2 $[^{89}\text{Zr}]\text{Zr-BI 754111}$ PET scan procedure

All PET scans will be performed on a PET/CT scanner (e.g. █████ Ingenuity TF). All patients will undergo whole body PET scans at various time points, e.g. $t = 72$ and $t = 144$ hours post-injection. The PET scans will be preceded by a 30 mAs low-dose CT, used for attenuation correction and anatomical localization of the PET-signal. Following CT, a total body PET scan will be acquired. PET scans consist of 10-12 bed positions, depending on the length of the patient, of various time lengths, usually 5 minutes each. Total acquisition time per scan, including low dose CT will be around 60 minutes.

PET data will be normalized and corrected for randoms, tissue attenuation, decay, scatter and dead time. PET-CT data will be reconstructed with TF-OSEM, resulting in a transaxial spatial resolution of ~ 7 mm in the centre of the field of view. Regions of interest (ROIs) will be defined using the CT images which are co-registered to the PET-CT data. ROIs around the organs which accumulate ^{89}Zr (e.g. liver, lung and other metastatic lesions) will be drawn manually directly on the PET images. All tissue concentrations will be related to the blood concentration (venous samples). The radioactivity concentrations in all regions for all imaging time points will be recorded digitally in a spreadsheet.

Quantitative accuracy of ^{89}Zr -PET scans was previously confirmed in █████ center using phantom studies and comparisons between PET-derived and biopsy tumor radioactivity concentrations ([R18-1538](#), [R18-1539](#)).

A blood sample (~ 6 mL) will be drawn *at four early time points post injection of $[^{89}\text{Zr}]\text{Zr-BI 754111}$ (after CTP 3.0) and at each $[^{89}\text{Zr}]\text{Zr-BI 754111}$ PET scan* to determine ^{89}Zr -kinetics based on measurements of radioactivity. See [Blood Sample Flow Chart](#) for time schedule. The detailed procedures of $[^{89}\text{Zr}]\text{Zr-BI 754111}$ PET/CT scanning will be described in the lab manual at the site.

Analysis of PET data:

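### The primary SUVpeak change pairs scans by nominal time point and ignores actual hours after injection, so, unless the withheld imaging windows are narrow, timing gaps can create or hide apparent blockade

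*SAP*

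**What the plan says.** **Formula (SAP 7.4.1).** For each patient the plan says: "Calculate the relative change from baseline for each selected lesion at each time point (e.g. 96h, 144h"). Each change is Cycle 2 minus Cycle 1 SUVpeak, divided by Cycle 1 SUVpeak. Changes are averaged over lesions at each time point and the lower mean is kept, so that "the time point leading to the maximum effect (max. reduction from baseline) will be reported".

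**Scan timing (protocol Flow Chart, footnotes 7 and 8).** Both cycles have the same rule: "2 (before CTP 3.0)-3(after CTP 3.0) scans between 24 h and up to 7 days post" injection. The pre-amendment Blood Sample Flow Chart (Tables 1 and 2) gives "≥24hours post [⁸⁹ Zr]Zr-BI 754111 PET scan 1" and "≤ 7 days post [⁸⁹ Zr]Zr-BI 754111 PET scan 2". Scan 1 thus has only a lower limit and scan 2 only an upper one.

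**Which version applies.** SAP 7.4.1 states that nobody was imaged under v3, so the v1/v2 rules apply.

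**Example times.** Protocol 5.6.2 says "All patients will undergo whole body PET scans at various time points, e.g". and names 72 and 144 h. SAP 7.4.1 names 96 and 144 h.

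**Other provisions.** SAP 6.7 refers to Table 6.7: 1 for nominal imaging times and windows; that table is not in the public text. Protocol 3.2 has the Study Monitoring Committee (SMC) confirm imaging times for each Part 2 patient. SAP 7.4.2 rules out any sensitivity or further exploratory analysis of the primary endpoint.

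**The concern.** The endpoint is meant to isolate what cold BI 754111 does to tracer uptake. Uptake also depends on time since injection, and the documents treat it so: Part 1 is partly there to optimise the imaging window (protocol 3.1), and Amendment 2 changed scan times to support kinetic modelling. PET data are decay-corrected (protocol 5.6.2), so what remains is the biological time course. If the two scans of a pair are taken at different hours, that time course enters the ratio. A late Cycle 2 scan hides blockade and an early one imitates it.

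Three features raise the stakes.

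- All lesions in a patient share the same scan times, so averaging over lesions does not dilute a timing error.
- A dose cohort may hold as few as 2 patients (protocol 3.1, 3.2), so one pair can carry half a cohort mean.
- Choosing the lower of two means does not treat errors symmetrically: scatter in either direction tends to come out as reduction.

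A mismatch inside the permitted range is not a protocol deviation, so the deviation review in SAP 6.2 need not find it.

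**Working it through.** The documents give no tracer kinetics and no figure to reproduce. The gap in step 1 follows from the protocol; the percentages in steps 2 to 4 rest on assumptions.

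**Step 1. Largest gap within a pair.** The protocol range under v1/v2 is 24 h to 7 days: 168 - 24 = 144 h. This is a theoretical outer limit. Given the example times of 72, 96 and 144 h, gaps of 24 to 48 h are the realistic case, and they are used below.

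**Step 2. Artefact with zero blockade.** Assume decay-corrected uptake S(t) = 1 - 2^(-t/h), with half-time h from 24 to 96 h. The spurious change is 100 × (S(t in Cycle 2)/S(t in Cycle 1) - 1).

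| h | S(72) | S(96) | S(144) | C1 96 h, C2 144 h | C1 96 h, C2 72 h |
|---|---|---|---|---|---|
| 24 h | 0.875 | 0.938 | 0.984 | +5.0% | -6.7% |
| 48 h | 0.646 | 0.750 | 0.875 | +16.7% | -13.8% |
| 72 h | 0.500 | 0.603 | 0.750 | +24.3% | -17.1% |
| 96 h | 0.405 | 0.500 | 0.646 | +29.3% | -18.9% |

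For example, at h = 48 h: 0.875/0.750 - 1 = +16.7%.

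Near the plateau the effect is small: 120 h against 144 h at h = 24 h gives 0.9844/0.9688 - 1 = +1.6%.

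**Step 3. Masking.** Take a true change of -30% (illustrative) with Cycle 1 at 96 h and Cycle 2 at 144 h. The observed change is 0.70 × S(144)/S(96) - 1:

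- h = 48 h: 0.70 × 1.167 - 1 = -18.3%
- h = 96 h: 0.70 × 1.293 - 1 = -9.5%

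**Step 4. Effect of keeping the lower mean.** Simulation with no blockade: scans nominally at 96 and 144 h, each with an independent uniform timing error, and the lower of the two changes kept.

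| Error per scan | h = 24 h | h = 48 h | h = 96 h |
|---|---|---|---|
| none | 0% | 0% | 0% |
| ±12 h, average | -0.8% | -2.0% | -3.1% |
| ±24 h, average | -1.6% | -4.0% | -6.0% |
| ±24 h, lowest 5% of patients at or below | -6.7% | -15.2% | -21.6% |

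At ±24 h a single pair at 96 h averages +0.1% to +1.1% over these half-times, so the negative shift comes from the selection.

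**Step 5. Can one pair reverse a two-patient mean?** Let both patients have true relative reduction b, and let one pair carry artefact a. The mean is positive only if (1 - b)(1 + a) - 1 > b, that is b < a/(2 + a). For a = 16.7%, b must be below 0.167/2.167 = 7.7%. For a = 29.3%, b must be below 0.293/2.293 = 12.8%. With a true -30% in both and h = 96 h, the mean is (-30 - 9.5)/2 = -19.75%: attenuated, not reversed.

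**The case against.** The strongest reply is that the governing rule is withheld, not absent. SAP 6.7 cites a table of imaging windows. If it confines scans to a few hours around 96 and 144 h, pairs are already matched closely enough. The SMC's confirmation of Part 2 times and the fixed 96h and 144h labels in the SAP's baseline summary also suggest settled times. This stands, and it makes the point conditional. It does not remove it: a window of ±w around a label bounds each scan separately and still allows a pair to differ by 2w.

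Second, every percentage depends on an assumed uptake curve. That stands too. If uptake has nearly plateaued by the first scan, little remains.

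Third, the endpoint is descriptive, and protocol 7.3 says all individual data will be listed. But a descriptive estimate can still be biased, and neither document asks for hours after injection by pair.

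Some stronger readings are tempting and are not supported:

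- A reader might infer that patients' scans were in fact days apart. The documents show only that the protocol permits it.
- A reader might apply the v3 windows, such as "Planned time ~+96 hours (within 4 to 7 days) post" injection, as the source of large gaps. No patient was imaged under v3.
- A reader might take 72 h against 96 h as a known mismatch within one patient. Both figures are examples, in different documents.

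**Conclusion.** The point holds in conditional form. On the visible text, the pairing uses labels only, v1/v2 does not match a patient's Cycle 2 scans to the Cycle 1 hours, and nothing planned would reveal a mismatch. Unless Table 6.7: 1 is narrow, gaps of 1 to 2 days could create or hide blockade. Over assumed half-times of 24 to 96 h the size is +5% to +29% (96 h then 144 h) or -7% to -19% (96 h then 72 h). Keeping the lower mean adds about -2% to -6% on average at ±24 h per scan, under independent uniform timing errors.

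A reader might go further and conclude that one mismatched patient reverses a small cohort's result. With two patients, this needs true blockade below about 8% to 13% for artefacts of +16.7% to +29.3%, so it cannot be claimed in general.

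**What to change.** - **SAP 7.4.1:** list actual hours after injection for every scan, with the difference between cycles for each pair. Keep the primary summary on all evaluable pairs.
- **SAP 7.4.2:** replace the statement that no sensitivity analysis will be done with one restricted to pairs within a stated maximum difference (for example 12 h), or adjusted for actual time. One adjustment is to interpolate the patient's two Cycle 1 scans to the Cycle 2 hour. A 12 h limit does not remove the artefact: 96 h against 108 h still gives 0.9558/0.9375 - 1 = +2.0% at h = 24 h, and 0.5415/0.5 - 1 = +8.3% at h = 96 h.
- **Protocol 5.6.2 and SAP 7.4.1:** reconcile the example scan times (72/144 h and 96/144 h).

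The cost is one listing and one table, with fewer pairs in the sensitivity analysis. The times should be recoverable, since radioactivity samples accompany the PET scans and protocol 5.3.2 requires actual blood sampling times to be recorded. Unmatched pairs should stay in the primary summary, because excluding them at an arbitrary limit could empty a two-patient cohort. SAP section 4 says the study was terminated early, so scheduling Cycle 2 scans at the patient's Cycle 1 hours matters only if further patients are imaged.
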